9. STATISTICAL METHODOLOGY

9.1 General

Summary statistics and figures by ethnicity (Japanese and non-Japanese) will be provided as appropriate.

Data listings will be provided for all data that is databased. Summary statistics and statistical analysis will only be presented for data where detailed in this SAP. For continuous data, summary statistics will include the arithmetic mean, arithmetic standard deviation (SD), median, min, max and N; for log-normal data (e.g. the PK parameters: area under the concentration versus time curve [AUC] and maximum observed drug concentration [C_{max}]) the geometric mean and geometric coefficient of variation (CV%) will also be presented. For categorical data, frequency count and percentages will be presented. Data listings will be provided for all subjects up to the point of withdrawal, with any subjects excluded from the relevant population highlighted. Summary statistics and statistical analyses will generally only be performed for subjects included in the relevant analysis population. For the calculation of summary statistics and statistical analysis, unrounded data will be used.

Mean change from baseline is the mean of all individual subjects' change from baseline values. Each individual change from baseline will be calculated by subtracting the individual subject's baseline value from the value at the timepoint. The individual subject's change from baseline values will be used to calculate the mean change from baseline using a SAS procedure such as Proc Univariate.

Data analysis will be performed using SAS® Version 9.4 or greater.

9.2 Demographics and Subject Disposition

Subject disposition will be listed. The demographic variables age, sex, race, ethnicity, country of enrolment, site ID, body weight, height and body mass index will be summarized by ethnicity (overall, Japanese and Non-Japanese) and listed. All other demographic variables will be listed only.

9.3 Pharmacokinetic Assessment

9.3.1 Pharmacokinetic Analysis

PK parameters for LY3478006 will be calculated by standard noncompartmental methods of analysis (NCA) using Phoenix/WinNONLIN. The primary parameters for analysis will be C_{max} and area under the concentration versus time curve from zero to infinity ($AUC_{0-\infty}$). Other noncompartmental parameters, such as halflife ($t_{1/2}$), total body clearance of drug (CL), volume of distribution during the terminal phase (V_z) (apparent clearance, and apparent volume of distribution for SC administration) may be calculated and reported as deemed appropriate.

Eli Lilly is responsible for the PK statistical analysis and reporting of data.

In addition, LY3478006 concentration time data may be analyzed using non-linear mixed effect modeling as implemented in software such as NONMEM. Serum data from all subjects will be pooled to determine the compartmental PK parameters (for example, CL, volume of distribution at steady state following IV administration [V_{ss}], $t_{1/2}$, bioavailability of drug [F]) and between-subject variability. Covariate relationships, such as CL or volume of distribution versus body size (for example, body weight and body mass index) or gender, may be investigated through graphical exploration and may be quantified through modeling. The effect of factors such as race/ethnicity (Japanese versus non-Japanese subjects) could be tested in the model and may be included in the final model.

9.3.2 Pharmacokinetic Statistical Methodology

PK parameter estimates from the NCA will be evaluated to delineate effects of dose proportionality. Log-transformed C_{max} and AUC estimates will be evaluated in a linear model with log-transformed IV dose as a fixed effect. The treatment differences will be back-transformed to present the ratios of geometric means and the corresponding 90% confidence intervals (CI). For the SC dose, the bioavailability relative to IV infusion at the same dose will be evaluated via a log-transformed model. The log-transformed C_{max} and AUC will be the response variable, and route of administration (IV/SC) is the explanatory variable.

Eli Lilly is responsible for the PK statistical analysis and reporting of data.

9.4 Safety and Tolerability Assessments

9.4.1 Adverse events

Where changes in severity are recorded in the Case Report Form (CRF), each separate severity of the adverse event (AE) will be reported in the listings, only the most severe will be used in the summary tables. A pre-existing condition is defined as an AE that starts before the subject has

provided written informed consent and is ongoing at consent. A non-treatment emergent AE is defined as an AE which starts after informed consent but prior to dosing. A treatment-emergent AE is defined as an AE which occurs postdose or which is present prior to dosing and becomes more severe postdose.

All AEs will be listed. Treatment-emergent AEs will be summarized by ethnicity (overall, Japanese and non-Japanese), treatment, severity and relationship to the study drug. The frequency (the number of AEs, the number of subjects experiencing an AE and the percentage of subjects experiencing an AE) of treatment-emergent AEs will be summarized by ethnicity (overall, Japanese and Non-Japanese), treatment, Medical Dictionary for Regulatory Activities (MedDRA) version 22.1 system organ class and preferred term. The summary and frequency AE tables will be presented for all causalities and those considered related to the study drug by the investigator. Any serious AEs will be listed.

Discontinuations due to AEs will be listed.

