Subjects will return to the CRU as outpatients at predetermined visits up to approximately 12 weeks postdose for safety assessment and collection of PK, pharmacodynamic (PD) biomarker, and immunogenicity samples. The follow-up period may be extended by adding up to 3 outpatient visits if necessary based on the emerging PK data. Subjects who do not develop treatment-emergent antidrug antibodies (TE-ADA), or whose ADA at the end of the follow-up period do not meet TE-ADA criteria, may be discharged from the study at the end of the follow-up period if deemed appropriate by the investigator. Subjects whose ADA meets the TE-ADA criteria at the end of the follow-up period will continue outpatient visits to monitor ADA until the signal returns to baseline or for up to 12 months after the end of the follow-up period (or early termination), whichever is sooner.

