Subjects will have up to a 4-week screening period, will be admitted to the clinical research unit (CRU) on Day -1, and their eligibility will be confirmed prior to dosing on Day 1. Subjects will remain resident in the CRU and may be discharged on Day 5 after all study procedures have been completed, at the discretion of the investigator. Subjects will return to the CRU as outpatients at predetermined visits up to approximately 12 weeks postdose for safety assessment and collection of PK, pharmacodynamic (PD) biomarker, and immunogenicity samples. Safety will be assessed by monitoring of AEs, clinical laboratory tests, vital signs (blood pressure and pulse rate), electrocardiograms (ECGs), directed neurological examinations, and pupillometry.

Subjects will be followed for 12 weeks based on a projected half-life of approximately 16 days. This follow-up period may be extended by adding up to 3 outpatient visits if necessary based on the emerging PK data, to ensure a follow-up duration of at least 5 half-lives (Section 2). Study activities for these additional visits will be the same as for the Day 85 visit. For subjects who do not develop treatment-emergent antidrug antibodies (TE-ADAs), or whose ADA at the end of the follow-up period do not meet TE-ADA criteria, they may be discharged from the study at the end of the follow-up period if deemed appropriate by the investigator. For subjects whose ADA meets the TE-ADA criteria at the end of the follow-up period, additional outpatient visits may be

required to monitor ADA until the signal returns to baseline (Section 9.7), or for up to 12 months after the end of the follow-up period (or early termination), whichever is sooner. Adverse events and blood samples for LY3478006 concentration should also be collected at these outpatient visits.

Study governance considerations are described in detail in [Appendix 3](#).

Abbreviations: IV = intravenous; LY = LY3478006; N = number of subjects; PBO = placebo; SC = subcutaneous.

Note: Figure is for illustration purposes only. Escalation to next cohort will take place following review of safety data up to Day 15.

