### **9.2.1. Serious Adverse Events**

An SAE is any AE from this study that results in one of the following:

- death
- initial or prolonged inpatient hospitalization
- a life-threatening experience (that is, immediate risk of dying)
- persistent or significant disability/incapacity
- congenital anomaly/birth defect
- important medical events that may not be immediately life-threatening or result in death or hospitalization but may jeopardize the patient or may require intervention to prevent one of the other outcomes listed in the definition above.

Study site personnel must alert the Lilly CRP/CP, or its designee, of any SAE as soon as practically possible.

Additionally, study site personnel must alert Lilly Global Patient Safety, or its designee, of any SAE within 24 hours of investigator awareness of the event via a sponsor-approved method. If alerts are issued via telephone, they are to be immediately followed with official notification on study-specific SAE forms. This 24-hour notification requirement refers to the initial SAE information and all follow-up SAE information.

Although all AEs are recorded in the eCRF after signing informed consent, SAE reporting to the sponsor begins after the subject has signed informed consent and has received IP. However, if an SAE occurs after signing informed consent, but prior to receiving IP, AND is considered Reasonably Possibly Related to a study procedure then it MUST be reported.

Investigators are not obligated to actively seek AEs or SAEs in subjects once they have discontinued from and/or completed the study (the subject summary CRF has been completed). However, if the investigator learns of any SAE, including a death, at any time after a subject has been discharged from the study, and he/she considers the event reasonably possibly related to the study treatment or study participation, the investigator must promptly notify Lilly.

Pregnancy (maternal or paternal exposure to IP) does not meet the definition of an AE. However, to fulfill regulatory requirements any pregnancy should be reported following the SAE process to collect data on the outcome for both mother and fetus.

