## 9.7. Immunogenicity Assessments

At the visits and times specified in the Schedule of Activities (Section 2), venous blood samples will be collected and stored for potential future analysis to determine antibody production against LY3478006. Antibodies may be further characterized for their ability to neutralize the activity of LY3478006. To interpret the results of immunogenicity, a venous blood sample will be collected at the same time points to determine the serum concentrations of LY3478006. All samples for immunogenicity should be taken predose when applicable and possible.

Treatment-emergent antidirug antibodies (TE-ADAs) are defined in Section 10.3.3. If the immunogenicity sample at the last scheduled assessment or discontinuation visit is TE-ADA positive, additional samples may be taken until the signal returns to baseline (i.e. no longer TE-ADA positive) or for up to 1 year after last dose.

Samples will be retained for a maximum of 15 years after the last subject visit, or for a shorter period if local regulations and ethical review boards (ERBs) allow, at a facility selected by the sponsor. The duration allows the sponsor to respond to future regulatory requests related to the IP. Any samples remaining after 15 years will be destroyed.

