### ***10.3.3. Evaluation of Immunogenicity***

Upon full assay validation, TE-ADAs will be assessed. The frequency and percentage of subjects with preexisting ADA and with TE-ADA to LY3478006 may be tabulated.

Treatment-emergent ADAs are defined as those with a titer 2-fold (1 dilution) greater than the minimum required dilution if no ADAs were detected at baseline (treatment-induced ADA) or those with a 4-fold (2 dilutions) increase in titer compared to baseline if ADAs were detected at baseline (treatment-boosted ADA).

The frequency of neutralizing antibodies may also be tabulated in TE-ADA+ subjects, when available.

The relationship between the presence of antibodies and the PK parameters and PD response may be assessed.

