### Protocol J2F-MC-OHAA Sampling Summary

Purpose	Blood Volume per Sample (mL)	Number of Blood Samples	Total Volume (mL)
Screening tests a	20.5	1	20.5
Clinical laboratory tests a,b	12.5	12	150
Pharmacokinetics b,d	3	17	51
Nerve growth factor b,d	0.5	17	8.5
Immunogenicity b,c,d	10	4	40
Pharmacogenetics	10	1	10
Non-pharmacogenetic storage samples	10	3	30
Total b,c,d			310
Total for clinical purposes (rounded up to nearest 10 mL)			310

a Additional samples may be drawn if needed for safety purposes.

b If 12 weeks is shorter than 5 half-lives of LY3478006 based on emerging pharmacokinetic data, up to 3 additional follow-up visits may be added, at each of which additional samples will be taken. An additional blood volume of 78 mL (37.5 mL for clinical laboratory tests, 9 mL for pharmacokinetics, 1.5 mL for nerve growth factor, and 30 mL for immunogenicity) would be collected if the subject attended the maximum allowed number of follow-up visits.

c In the event of drug hypersensitivity reactions (immediate or non-immediate), 3 additional samples will be collected for immunogenicity (a total additional blood volume of 30 mL [one 10-mL sample collected as close to the onset of the event as possible, one 10-mL sample collected at the resolution of the event, and one 10-mL sample collected 30 days following the event]).

d If the immunogenicity sample at the last scheduled assessment or discontinuation visit is TE-ADA positive, up to 4 additional outpatient visits may be required to monitor ADA until the signal returns to baseline (e.g., no longer TE-ADA positive) or for up to 1 year after the last dose. An additional blood volume of 54 mL (12 mL for pharmacokinetics, 2 mL for nerve growth factor, and 40 mL for immunogenicity) would be collected if the subject attended outpatient visits for 1 year after the last dose.

---

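### SAP 9.4.1 gives treatment-emergent AEs no end date, so the TEAE tables would compare drug and placebo over unequal time if any subject stays on for antidrug-antibody monitoring

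*SAP*

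**What the plan says.** **The definition and the table.** SAP 9.4.1 reads "A treatment-emergent AE is defined as an AE which occurs postdose", and adds AEs present before dosing that become more severe afterwards. No closing day, visit or person-time adjustment appears there or elsewhere in the SAP. TEAEs are tabulated by treatment and ethnicity as event counts, subjects affected and percentage affected. Protocol Table OHAA.1 makes the frequency of SAEs and TEAEs the primary endpoint.

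**A bound that is mentioned but never set.** The TEAE entry in Protocol Appendix 1 ties the term to a treatment period that it treats as defined. Neither document defines that period. The SAP wording drops the phrase, and SAP 12 reports no change from the protocol's analyses.

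**Who is observed for longer.** Protocol 5.1 follows all subjects for 12 weeks. The Synopsis then says "Subjects whose ADA meets the TE-ADA criteria at the end of the follow-up period will continue outpatient visits to monitor ADA"; Section 5.1 says only that such visits may be required. Section 5.1 adds "Adverse events and blood samples for LY3478006 concentration should also be collected at these outpatient visits". Monitoring ends when the signal returns to baseline. Otherwise it lasts "for up to 12 months after the end of the follow-up period" in Section 5.1, or "for up to 1 year after last dose" in Section 9.7. Appendix 4, footnote d, says "up to 4 additional outpatient visits may be required to monitor ADA until the signal returns to baseline".

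**Who is not.** Subjects who do not meet the criteria may be discharged at the end of follow-up if the investigator thinks it appropriate. After that, Protocol 9.2.1 applies: "Investigators are not obligated to actively seek AEs or SAEs in subjects once they have discontinued from and/or completed the study".

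**The concern.** Taken as written, an AE at month 10 in a subject kept on for ADA monitoring enters the same table as subjects who were observed for 84 days. Whether a subject is kept depends on a response measured after dosing, so randomization does not balance it. Antibodies to LY3478006 should arise mainly in subjects who received it (an assumption; the documents give no TE-ADA rate), so the extra time would fall mostly in the drug columns.

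At stake is how the primary safety table is read. The percentages are crude and descriptive, and nothing in the analysis corrects for time. A drug column with one or two long-observed subjects could show more events than placebo for that reason alone. Small columns are the most exposed, such as the 3 Japanese drug subjects planned per dose in Cohorts 3 to 6.

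**Working it through.** **Plan figures first.** 7 cohorts × 8 = 56 planned completers, as stated: 42 on drug (7 × 6) and 14 on placebo (7 × 2). Five projected half-lives are 5 × 16 = 80 days, which fits within the 12-week (84-day) follow-up.

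**Inputs from the documents**
- Scheduled follow-up: Day 1 to Day 85, 84 days.
- Maximum under Section 5.1: 84 + 365 = 449 days. Maximum under Section 9.7: 365 days. Both are ceilings, because monitoring stops when ADA returns to baseline.
- AE review days from dosing in the Schedule of Activities: 1, 2, 3, 5, 8, 10, 15, 22, 29, 43, 57, 71, 85, which is 13.
- Extra ADA visits: up to 4 (Appendix 4, footnote d).
- Drug subjects per dose group: 6.

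**Assumptions.** The documents give no AE rate. I take the same underlying rate on drug and placebo, one drug subject extended, none on placebo, and no dropouts.

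**Step 1. Multiplier m for the extended subject's expected AE count**
- Recording follows visits: (13 + 4)/13 = 1.31.
- Half the core daily rate after Day 85: 1 + 0.5 × (365 − 84)/84 = 2.67, to 1 + 0.5 × (449 − 84)/84 = 3.17.
- Constant daily rate: 365/84 = 4.35, to 449/84 = 5.35.

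**Step 2. Ratio of expected AE count to that of a group observed for 84 days**

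| Recording after Day 85 | Group of 6: (5 + m)/6 | Group of 3: (2 + m)/3 |
|---|---|---|
| Follows visits | 1.05 | 1.10 |
| Half rate, full extension | 1.28 to 1.36 | – |
| Constant rate, full extension | 1.56 to 1.72 | 2.12 to 2.45 |

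**Step 3. Percentage of subjects with a TEAE, group of 6.** If a share p has an AE within 84 days, the expected percentage is [5p + 1 − (1 − p)^m]/6.
- p = 30%: 31.2% by visits, 35.2 to 36.3% at half rate, 38.1 to 39.2% at constant rate.
- p = 50%: 51.6%, 55.7 to 56.5%, and 57.5 to 57.9%.

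For p = 30% the shift is between 6 × 0.012 = 0.07 and 6 × 0.092 = 0.55 of a subject. One subject in 6 is 16.7 percentage points, so even the ceiling is less than one subject.

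**Step 4. With a common window.** Planned observation is 84 days in every column, and the ratio is 1.0.

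**The case against.** The strongest reply is that several things must happen before anything changes. Protocol 9.7 stores ADA samples for potential later analysis, and Section 10.3.3 says "Upon full assay validation, TE-ADAs will be assessed". A subject must then meet the criteria at the end of follow-up, be kept on, and have a new or worsened AE after it. The chance of all this cannot be estimated from the documents. This stands, and it is why the point is conditional.

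The tables are also descriptive. SAP 9.4.15 plans no inferential analysis, all AEs are listed, and related TEAEs are tabulated separately, so a late event can be traced to its subject. Dose escalation requires safety data only through at least Day 15. This stands too: no error rate or escalation decision is affected.

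An open window is, moreover, the inclusive choice in a first-in-human antibody study. Schedule of Activities footnote i asks for additional safety assessments in TE-ADA subjects, where late events are of interest. That argues against dropping those AEs from view. It does not argue against a comparison over common time. The TFL shells, which were not available, might set a window; the SAP text does not.

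A reader might also infer three stronger things that the documents do not support:
- **That only TE-ADA subjects stay on.** Discharge of the others is at the investigator's discretion. The rule also goes by ADA status and not by arm, so a qualifying placebo subject would be kept as well.
- **That ratios of 1.56 to 2.45 are the likely effect.** They need ADA that never returns to baseline, and AE capture in the extension, over at most 4 visits, as intensive as in the core period.
- **That the PK-driven extension in footnote m adds a drug-versus-placebo imbalance.** It lengthens both arms of a cohort alike. It could matter only between cohorts and against the pooled Placebo IV column, and at the projected half-life (80 days against 84) it is not expected.

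**Conclusion.** The gap is real. The SAP opens the TEAE window and never closes it, the protocol continues AE collection selectively after scheduled follow-up, and the period mentioned in Appendix 1 is not defined. If any subject is extended, the crude primary TEAE tables mix unequal observation times, weighted toward drug on the assumption that TE-ADA arises almost entirely in treated subjects.

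The size is zero if nobody is extended and probably small otherwise. For one extended subject in a group of 6, the AE-count ratio is about 1.05 if recording follows visits; 1.56 to 1.72 is a ceiling. Those figures rest on equal underlying AE rates and no dropouts. It would be wrong to conclude that the primary safety result is biased: the documents do not show that anyone will be extended. Treat this as a low-priority, conditional improvement.

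**What to change.** In SAP 9.4.1, base the drug-versus-placebo TEAE frequency table on onset or worsening from dosing through the scheduled follow-up that applies to all subjects in the cohort regardless of ADA status. That means the Day 85 or early-termination visit, or the last PK-extension visit if footnote m is applied to that cohort. Then do one of two things with later AEs:
- show them by treatment in a separate summary or listing; or
- keep the all-postdose table as a flagged supplement.

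Apply no cut-off to SAEs. Early terminations will still shorten some subjects' time; the change removes only the imbalance created by ADA-only monitoring.

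The cost is a short SAP edit and one extra table or listing, with no protocol change and no new data. The drawback is that late non-serious AEs appear beside the main comparison and not in it. The separate display by treatment keeps them visible.

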9.4.2 Concomitant medication

Concomitant medication will be coded using the World Health Organization (WHO) drug dictionary (Version September 2019). Concomitant medication will be listed.

9.4.3 Clinical laboratory parameters

All clinical chemistry and hematology data will be summarized by parameter and treatment, and listed. Urinalysis data will be listed. Additionally, clinical chemistry, hematology and urinalysis data outside the reference ranges will be listed and flagged on individual subject data listings.

